2.4.2. SECONDARY & TERTIARY OUTCOMES

The secondary outcome measures include:

- DCCT-aligned HbA1c (local assays);
- LDL cholesterol (central assay);
- Albuminuria (as per Protocol Appendix 5.0)
- Estimated glomerular filtration rate (eGFR) (ml/min/1.73m² by MDRD equation);
- Retinopathy stage (ETDRS) (two or more step progression, concatenated score from baseline);

- Weight (kg);
- Insulin dose per 24 hours per kg (units/kg);
- Endothelial function (Reactive Hyperaemia Index by peripheral arterial tonometry).*

*This measurement is only collected in a subset of centres with available equipment.

Each of the above secondary outcome measures will be analysed separately and the individual results will be reported. The protocol has a pre-defined composite interpretation of all secondary outcomes, where results will be considered as clinically meaningful with the potential to influence clinical practice only in the event that a statistically significant improvement in two or more of the individual secondary outcomes is observed on metformin.

Tertiary outcomes include:

- Frequency of major hypoglycaemia (per patient-year) (Steno Questionnaire);
- Frequency of minor hypoglycaemia (per patient-year) (Steno Questionnaire)
- Treatment satisfaction (Diabetes Treatment Satisfaction Questionnaire);
- Progression of averaged maximal distal IMT of the common carotid artery at 12, 24 and 36 months;
- Occurrence of biochemical Vitamin B12 deficiency, defined as values of vitamin B12 < 150pmol/L reported in the lab data in the eCRF.

All secondary and tertiary outcomes will be analysed using the relevant mITT analysis set.

All continuous secondary and tertiary outcomes will be summarised, overall and by treatment group at each time point; change from baseline will also be summarised. Non-Normally distributed variables will be transformed first. Repeated measures models will be applied to all continuous secondary and tertiary outcomes (except for the tertiary outcome “Progression of averaged maximal distal common carotid artery IMT” which will be analysed as per the primary outcome, using the maximal far wall IMT measurements as the main analysis, calculated as detailed below), assuming a general residual covariance structure, with the change from baseline as the outcome, and predictor variables of treatment, visit number (included as a class variable) and the outcome baseline level where available. The main analyses will test the significance of and provide an estimate of the main effect of treatment in this model. The treatment effect estimate, corresponding 95% confidence interval and p-value will be reported.

As an exploratory analysis to investigate whether the treatment effect varies over time, a visit by treatment interaction term will be added to each model and tested for significance. The p-value for the interaction term will be reported. In addition, the treatment effect, 95% confidence interval and p-value will be reported for each visit.

The main analysis of the averaged maximal distal IMT of the common carotid artery will use solely the maximum far wall cIMT measurements, and unlike the main analysis of the primary outcome, will not restrict to values < 1.5mm. A sensitivity analysis will also be performed using both the maximum near wall and the maximum far wall measurements as detailed in section 2.4.3.

The calculation of the averaged maximal distal IMT at each time point will use the following hierarchy:

1. Use all available data for the maximum far wall IMT regardless of data availability at other time points.

2. In instances where any duplicate angles are included (resulting in more than six angles per time point), average these duplicate angles first to result in one single measurement per angle.
3. Average next the angles within each side to result in one single measurement for each of the left and right sides
4. Average the remaining left and right measurements to obtain one result per time point

The frequency of hypoglycaemia will be analysed using a Negative-Binomial regression model, accounting for over-dispersion using the scale option, with the logarithm of time as an offset variable. The frequency of the minor hypoglycaemia will be further adjusted for the method of collection, with results provided for all collection methods combined. Each method of collection will then be analysed and reported separately. In instances where there has been a change in the method of collection, the method that was most commonly used for each subject will be adjusted for.

New onset microalbuminuria will be analysed in a time to event analysis using a Cox Proportional Hazards Model. The results will be summarised graphically using the Kaplan-Meier method. Similar methods will be used to analyse the first occurrence of biochemical vitamin B12 deficiency.

For the retinopathy outcome, logistic regression analysis will be performed. If the numbers of patients with retinopathy are too small to allow logistic regression analysis to be performed, Fisher's exact test will be used instead.

The regression model for the primary outcome will be extended to determine if glucose-and/or lipid-lowering effects of metformin could potentially explain differential effects on the progression of cIMT. This will be accomplished by including baseline and on-treatment HbA1c and LDL-cholesterol values as time-dependent covariates in the model described above for the primary outcome.

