5. OBJECTIVES

Primary objective: to test for the first time in a double-blind randomized, placebo controlled trial whether three years treatment with metformin 1000 mg bd added to titrated insulin therapy (towards target HbA1c 7.0%/ 53 mmol/mol) reduces atherosclerosis, as measured by progression of carotid IMT, in adults with confirmed T1DM aged 40 years and over and at increased risk for CVD.

Secondary and tertiary objective: to examine over this period the effect of metformin on other markers of diabetic micro- and macrovascular complications and intermediate disease- related biomarkers. The composite secondary endpoint will provide clinically meaningful information on the potential of metformin to influence clinical practice in this condition. The REMOVAL study will be five times larger and three times longer than any previously-conducted trial of metformin in T1DM.

In REMOVAL, participants will be provided with the best care possible throughout the five-year follow-up period. They will be encouraged and supported to work towards and maintain target glycaemic control (HbA1c < 7.0%/ 53 mmol/mol) independent of the randomization (i.e. metformin or placebo). This will be achieved by: (i) increased attention to lifestyle measures; (ii) careful supported adjustment of insulin doses; and (iii) intensifying insulin regimens and doses where necessary.

The primary, secondary and tertiary endpoints are defined below.

Primary endpoint: progression of averaged mean far wall common carotid artery IMT (CCA cIMT, measured in mm, at baseline, 12, 24 and 36 months).

Secondary endpoints:

- (i) HbA1c;
- (ii) LDL cholesterol;
- (iii) albuminuria & estimated glomerular filtration rate
- (iv) retinopathy stage (ETDRS stage = Early Treatment Diabetic Retinopathy Study);
- (v) weight
- (vi) insulin dose;
- (vii) endothelial function (in some centres).

N.B. We will consider a statistically significant improvement in two or more of these secondary endpoints to be a clinically meaningful result with the potential to influence clinical practice.

Tertiary endpoints: To compare between treatment groups, as above, change in:

- (i) frequency of hypoglycaemia;
- (ii) treatment satisfaction;
- (iii) markers of endothelial function (t-PA, sE-selectin, sICAM-1);
- (iv) progression of averaged maximal distal common carotid artery IMT (CCA cIMT, measured in mm, at baseline, 12, 24 and 36 months).
- (v) vitamin B12 status

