Other endpoints: The sample size for the study is based on the primary endpoint as described above. This sample size also yields 90% power at 5% significance level to detect differences of approximately 0.3 SD in continuous outcomes i.e. lipid, metabolic and endothelial function parameter changes from baseline at follow up. To put this into context, in the largest trial of metformin in T1DM to date the reported effects on LDL-C were considerably larger than this at (0.46 SD) so that we have ample power to replicate and refine the precision of this treatment effect. For other endpoints we acknowledge that power is lower but emphasize that the sample size is appropriately based on the primary endpoint, and that we are stating *a priori* that we will consider a change in two of the seven secondary endpoints to be clinically meaningful. Thus, for retinopathy progression, based on recent data from the Wisconsin Epidemiologic Study of Diabetic Retinopathy (Co-applicant [name]) we expect three year two-step progression in categorical ETDRS retinopathy stage to be 13.7%. Assuming follow-up retinal photographs in 400 participants, treatment with metformin would have to be associated with a hazard ratio of 0.40 to have 80% power to declare significance for this specific secondary endpoint (at $p < 0.05$). Given the relatively low marginal cost of acquiring the retinal photographs, many of which will be captured from routine screening, we believe incorporation of this endpoint in the study is an opportunity to acquire at least a useful point estimate for likely effect size (albeit with wide confidence intervals). This may be

useful in assessing the statistical power of any future retinopathy intervention trials with metformin.

e) Feasibility of achieving required sample size

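### The two-or-more secondary rule is set on seven endpoints in the protocol but applied to eight outcomes in the SAP, so albuminuria and eGFR alone could meet it

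*SAP*

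**What the plan says.** Protocol Section 5 lists seven secondary endpoints, (i) to (vii). Item (iii) is "albuminuria & estimated glomerular filtration rate". Below the list it states the rule: "We will consider a statistically significant improvement in two or more of these secondary endpoints to be a clinically meaningful result". Section 6(d) repeats it with an explicit denominator: "we will consider a change in two of the seven secondary endpoints to be clinically meaningful".

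SAP 2.4.2 gives albuminuria and eGFR a bullet each. With HbA1c, LDL cholesterol, retinopathy stage, weight, insulin dose and endothelial function, the list has eight entries. It adds: "Each of the above secondary outcome measures will be analysed separately and the individual results will be reported". It then describes the rule as pre-defined in the protocol and requires that a "statistically significant improvement in two or more of the individual secondary outcomes is observed on metformin". The two renal measures also have different models in the same section: a Cox model for new-onset microalbuminuria, and the repeated measures model for continuous outcomes, which covers eGFR.

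SAP 1.6.4 names one departure from the protocol, the late biomarker assays. Neither document gives a multiplicity method or an error rate for the rule.

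**The concern.** The rule decides whether the secondary results may be described as clinically meaningful and able to influence practice. Neither document makes it conditional on a positive primary result, so it could support a favourable conclusion even if cIMT shows no difference.

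The SAP presents the rule as the protocol's but changes what is counted. Under the protocol, item (iii) can supply at most one of the two improvements needed, so the second must come from a different endpoint. Under the SAP, two markers of one organ system are enough. The requirement for breadth is weakened, and a reader who compares the report with the protocol would find a count that does not match.

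**Working it through.** **Inputs.** Seven endpoints (Protocol 5 and 6(d)); eight outcomes (SAP 2.4.2); 5% significance level and 200 per arm (Protocol 6(d)); LDL effect 0.46 SD from the largest earlier metformin trial in type 1 diabetes (Protocol 6(d)). Two assumptions are not in the documents: the 5% is two-sided, so each test has a 2.5% chance of a false improvement; and the correlation between tests, taken as 0 with a range shown.

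**The plan's own figure.** No error rate is stated for the rule, so there is none to reproduce. The nearest stated figure is 90% power at 200 per arm for 0.0167 mm with SD 0.05 mm. The standardised difference is 0.0167/0.05 = 0.334, and Φ(0.334 × √100 − 1.96) = 91.6%. This agrees with the stated 90%. A one-sided 5% test would give 95.5%, so the two-sided reading fits better.

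**No true effect, independent tests.** P(X ≥ 2) with X binomial:

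- seven tests: 1 − 0.975⁷ − 7 × 0.025 × 0.975⁶ = 1 − 0.8376 − 0.1503 = 1.2%
- eight tests: 1 − 0.975⁸ − 8 × 0.025 × 0.975⁷ = 1 − 0.8167 − 0.1675 = 1.6%

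The part of the 1.6% in which the renal pair is the only pair is 0.025² × 0.975⁶ = 0.05%. The pairing therefore matters for what the rule means, and hardly at all for its error rate under independence.

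**Exactly one true effect, detected.** LDL is the natural example: its power is Φ(0.46 × √100 − 1.96) = 99.6%. The rule is then met if any remaining null test shows a false improvement:

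| Correlation among null tests | Six remaining (seven in all) | Seven remaining (eight in all) |
|---|---|---|
| 0 | 1 − 0.975⁶ = 14.1% | 1 − 0.975⁷ = 16.2% |
| 0.2 | 12.9% | 14.7% |
| 0.4 | 11.3% | 12.6% |
| 0.5 | 10.4% | 11.5% |

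The eighth test adds 16.2 − 14.1 = 2.1 points if independent, and 1.3 points at correlation 0.4.

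**What the seven-endpoint figures presuppose.** They take one test per item. If both renal tests are kept and either may score the single renal count, a true LDL effect still leaves seven null tests, so the figure stays at 16.2%. With no true effect the rate is 1.6% − 0.05%, about 1.5%. Counting the pair once restores the protocol's rule; it does not by itself lower the one-true-effect figure.

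**What a Holm adjustment would cost.** Power for a 0.3 SD effect at 200 per arm is Φ(0.3 × √100 − 1.96) = 85% unadjusted. It is 62% at Holm's first step with seven tests (0.05/7) and 64% at the next (0.05/6). For LDL at 0.46 SD it falls only from 99.6% to 97%.

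**The case against.** The best reply is that nothing has really changed. Albuminuria is recorded as a positive or negative status and eGFR is continuous. The protocol defines no combined test for item (iii), so two tests may always have been implied. This stands as far as testing goes, and separate analysis of the two is not the problem. It does not settle the counting: however item (iii) is tested, the protocol counts it as one of seven.

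A reader might also infer that the SAP's eighth test creates a 16% false-positive risk. The documents do not support that. Seven tests already give 14.1%, so nearly all of the figure comes from unadjusted testing. It also needs exactly one real effect. The protocol cites earlier reductions in insulin dose (6.6 units/day) and weight (1.74 kg) as well as the LDL effect; if two or more effects are real and detected, the rule is met correctly and the figure does not apply. On the other side, Protocol 3.1 says the pooled data on HbA1c, weight and cholesterol were insufficient for confidence, so a single real effect remains a plausible case.

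Finally, the rule already restricts claims: one significant secondary outcome is not enough, and with no true effect the rule is rarely met. That stands, and it is why a familywise correction on top of the two-endpoint requirement is not demanded here.

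**Conclusion.** The mismatch is real. The protocol's rule has seven endpoints, the SAP applies it to eight, the SAP does not declare the difference, and the two renal measures alone could meet it. This is an error in a prespecified decision rule; the primary analysis is unaffected.

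Its effect on error rates is modest: about 1.2% against 1.6% with no true effect, and about 14% against 16% with exactly one true, detected effect, or 11% against 13% at correlation 0.4. These figures rest on two-sided 5% tests, one test per counted item and, for the 14% and 16%, independence. The documents give no correlations. The figures do not show that the rule is unsound or that a multiplicity correction is needed; they show what a reader should know when the rule is applied.

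**What to change.** State in SAP 2.4.2 that albuminuria and eGFR are analysed and reported separately but together count at most once towards the rule, so that it applies to the protocol's seven endpoints. If eight is intended, list it in SAP 1.6.4 as a deviation, with a reason, before unblinding.

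Beside the rule, give its error rate under no true effect and under one true effect, with the assumptions above, and say whether one or two renal tests can score the renal count.

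The cost is a few sentences. No model, estimate, interval or data collection changes. Judging significance for the rule by Holm-adjusted p-values is an option for the sponsor to weigh, given the loss of power for a 0.3 SD effect from about 85% to about 62–64%; it is not a requirement of this point.

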9. TIMELINE FOR PARTICIPANT IN STUDY

10. CLINICAL MEASUREMENTS AND EXAMINATIONS AT EACH VISIT

Prescreening visit. Provision of Patient Information Sheet and Expression of Interest form. Request for permission to contact.

Screening Visit (R1 start of Run-in Period) – non-fasting: Informed consent requested: if provided, full medical history, vital signs, weight, waist circumference, height measurements. Dispense study medication (which will be commenced following telephone prompting at visit R4). Give out diary. Treatment satisfaction questionnaire. Hypoglycaemia questionnaire. Titrate insulin. Blood samples (U&E, LFT, HbA1C, local laboratory total cholesterol, HDL and triglycerides, FBC, vitamin B12, C-peptide, microalbuminuria status. Samples for LDL, plasma biomarkers. Urine aliquot. Pregnancy testing if appropriate. Concomitant medications recorded. Review requirement for statin or ACE inhibitor against local practice, national guidelines and standard-of-care.

Telephone visits (R2-R4): insulin dose titration. Questions on adverse events. Visit R4 only: commence study medication.

Study Visit 1 (randomization): Vital signs, weight, waist circumference. Carotid IMT (can be done during last four weeks of Run-In). Retinal imaging. Endothelial function. Collect/ count unused medication. Dispense study medication with advice on dose titration. Give out diary. Hypoglycaemia questionnaire. Treatment satisfaction

questionnaire. Insulin dose titration/ record insulin dose. Blood samples (U&E, LFT, HbA1C, local laboratory total cholesterol, HDL and triglycerides, FBC, vitamin B12, microalbuminuria status if not available from Screening visit R1). Samples for LDL, plasma biomarkers. Lactate. Urine aliquot. Pregnancy testing if appropriate. Concomitant medications recorded. Questions on adverse events. Randomisation.

Telephone Visits 2-4 (0–1 month). Insulin dose titration/ record insulin dose, study medication dose titration (except at telephone visit 4). Questions on adverse events. Concomitant medications and Hypoglycaemia questionnaire (visit 4 only).

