2.3. BASELINE CHARACTERISTICS

In the ITT population, as a whole and by treatment group, summaries will be provided of the following baseline characteristics as included in the eCRF:

- Age and sex;
- ethnicity;
- smoking and alcohol habits;
- SBP, DBP and heart rate;
- height, weight, BMI and waist circumference;
- time since diabetes diagnosis;
- medical history – macrovascular, microvascular and other;
- family medical history (CV disease and diabetes);
- insulin regimen, including pump therapy;
- concomitant medications – statins, ACE-inhibitors, ARBs, antiplatelet and beta-blockers;
- treatment satisfaction questionnaire;
- hypoglycaemic events – minor and major;
- blood tests – creatinine, eGFR, capillary glucose (3-day average of each of: before breakfast, before mid-day meal, before evening meal and before bed) and C-peptide;
- average mean far wall cIMT (mm) of the common carotid artery;
- Lipid Assays – LDL cholesterol, HDL cholesterol, Total cholesterol and Triglycerides.

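### The hypoglycaemia rate models omit the participant's own pre-randomisation count, which is already collected; this costs some precision, mainly for minor events

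*SAP*

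**What the plan says.** SAP 2.4.2 lists the frequencies of major and minor hypoglycaemia, from the Steno questionnaire, as tertiary outcomes. The model reads: "The frequency of hypoglycaemia will be analysed using a Negative-Binomial regression model". Over-dispersion is handled by a scale factor, and log time is the offset. One further covariate is named, for minor events only: "The frequency of the minor hypoglycaemia will be further adjusted for the method of collection". No baseline hypoglycaemia term appears.

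The same section has a baseline rule for continuous outcomes. Their repeated measures models use "predictor variables of treatment, visit number (included as a class variable) and the outcome baseline level where available". Hypoglycaemia is a count with a separate model, so that rule does not reach it.

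The baseline data exist. Protocol section 10 lists, for the screening visit R1, "Give out diary. Treatment satisfaction questionnaire. Hypoglycaemia questionnaire", and lists the hypoglycaemia questionnaire again at Visit 1, the randomisation visit. The study diary also records episodes during run-in (Protocol 7.3(d)). SAP 2.3 tabulates "hypoglycaemic events – minor and major" among the baseline characteristics.

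**The concern.** People with type 1 diabetes differ widely in how often they have hypoglycaemia. If those differences persist from run-in to follow-up, part of the over-dispersion in the on-treatment counts is predictable from the run-in count. A model without that count leaves the predictable part in the residual variation, widens the interval for the rate ratio, and does not correct chance imbalance between arms in baseline rates.

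This has some practical weight because hypoglycaemia is part of the rationale for metformin (Protocol synopsis) and a stated risk in combination with insulin (Protocol section 8). SAP 2.4.5.4 also lists major hypoglycaemic events, but without formal testing. The negative-binomial models are therefore the only formal comparison of hypoglycaemia between arms.

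**Working it through.** **Plan's own figure.** There is none to reproduce. Protocol 6(d) gives power for cIMT, continuous outcomes and retinopathy, but no rate, dispersion or precision for hypoglycaemia.

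**Inputs from the documents.** 200 per arm, run-in of 3 months, follow-up of 3 years, and loss of 20-25% (20% early exit was used).

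**Assumed inputs.** Minor events 12-50 per year with dispersion k = 1-2. Major events 0.1-1.0 per year with k = 3. Correlation ρ between a person's run-in and on-treatment rates from 0 to 0.9.

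**Step 1, approximate formula.** Per person, the variance of the log rate is about 1/μ + k, where μ is the expected follow-up count. With the baseline count in the model it becomes 1/μ + k(1 − ρ²R). Here R = k/(k + 1/m) is the reliability of the run-in count and m is its expected value.

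- Minor, 12 per year, k = 1, ρ = 0.7: μ = 36, m = 3, R = 1/(1 + 1/3) = 0.75. Without the term: 0.0278 + 1 = 1.0278. With it: 0.0278 + (1 − 0.49 × 0.75) = 0.6603. The standard error (SE) ratio is √(0.6603/1.0278) = 0.80.
- Major, 0.1 per year, k = 3, ρ = 0.7: μ = 0.3, m = 0.025, R = 3/(3 + 40) = 0.070. Without the term: 3.333 + 3 = 6.333. With it: 3.333 + 3(1 − 0.49 × 0.070) = 6.231. The SE ratio is 0.99.

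The contrast is explained by R: a three-month count of a rare event is nearly always zero and carries little information.

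**Step 2, simulation with a 3-month run-in count.** There were 100 trials per scenario, with correlated log-normal person effects and no treatment effect. A negative-binomial model with log-time offset was fitted without and with log(run-in count + 0.5). The entries are the mean model-based SE with the term divided by the mean SE without it, which is also the ratio of interval widths on the log scale.

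| Events per year, k | ρ = 0 | ρ = 0.5 | ρ = 0.7 | ρ = 0.9 |
|---|---|---|---|---|
| Minor 12, k = 1 | 1.001 | 0.940 | 0.869 | 0.763 |
| Minor 50, k = 1 | 1.001 | 0.906 | 0.793 | 0.615 |
| Minor 50, k = 2 | 1.001 | 0.905 | 0.794 | 0.596 |
| Major 0.1, k = 3 | 1.001 | 0.999 | 0.993 | 0.993 |
| Major 0.3, k = 3 | 1.001 | 0.996 | 0.982 | 0.971 |
| Major 1.0, k = 3 | 1.003 | 0.979 | 0.960 | 0.913 |

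The variance cut is 1 − ratio².

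- Minor, ρ = 0.5: 1 − 0.940² = 12% to 1 − 0.905² = 18%.
- Minor, ρ = 0.7: 1 − 0.869² = 24% to 1 − 0.793² = 37%.
- Minor, ρ = 0.9: 42% to 64%. This is best read as a ceiling, because insulin regimens are being changed during run-in.
- Major: at most 1 − 0.960² = 8% at ρ = 0.7 and 1 − 0.913² = 17% at ρ = 0.9.

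**Step 3, simulation with a 4-week baseline window.** There were 60 trials per scenario, with minor events at 0.5-2 per week. Median variance ratios were:

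- 0.73, 0.68 and 0.63 at 0.5, 1 and 2 events per week, with log-scale person SD 0.8 and period SD 0.5;
- 0.52 with strong persistence (SDs 1.0 and 0.4);
- 0.89-0.90 with weak persistence (SDs 0.7 and 0.8).

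The cuts are therefore about 10% to 48% (1 − 0.52). If the period component is drawn afresh in each period, the central SDs imply ρ = 0.64/(0.64 + 0.25) = 0.72, so this agrees with Step 2. For major events the ratios were 0.95 and 0.87 with a 4-week window. The most favourable case, with 13 weeks, gave 0.75.

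**Step 4, cost if the assumption fails.** At ρ = 0 the SE ratio is 1.001-1.003.

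**The case against.** The case for leaving the SAP alone has several parts.

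- **Importance.** The outcomes are tertiary and do not enter the rule that two or more secondary outcomes must improve. Baseline imbalance would be visible in the baseline table. This stands, and it limits the severity.
- **Coherence.** A reader might infer that the SAP breaks its own baseline rule. It does not, because the rule is confined to continuous outcomes, and the Cox and logistic models also name no baseline severity term. The plan is consistent but less efficient than it could be.
- **Size.** All rates, dispersions and correlations are assumed. Run-in is when insulin is reviewed and regimens may be switched (Protocol 7.3(d) and (h)), which could weaken persistence. This stands. At correlation 0.5 the minor-event interval narrows by only 6 to 9%.
- **Fidelity.** The simulations do not include the collection-method term or the scale option. If method tracks reported frequency, that term already absorbs some between-person variation and the gains above are somewhat high. This stands.
- **Recall window.** The questionnaire (Protocol Appendix 3) counts events since the last contact, which is not a fixed period. It is not scheduled at R2-R4, but telephone contacts occur then. The Visit 1 count may therefore cover about 4 weeks or about 3 months. The R1 count has no study contact at which counting began. The fix must deal with this.

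None of this gives a reason to omit the term. It makes the gain smaller and less certain, and Step 4 shows that the downside is negligible.

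**Conclusion.** The omission is real, and its consequence is a loss of precision. Severity is low, and confidence in the magnitude is moderate.

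For minor events the baseline term would cut the variance of the log rate ratio by about 10 to 48%, depending on how strongly a person's rate persists. For major events the gain is usually a few percent (SE ratio 0.91-1.00 in the 3-month simulation). A cut of about 25% appears only in the most favourable simulated case.

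Three stronger readings are tempting but not supported:

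- *The treatment effect is biased or the test invalid.* With a log link the rate ratio is collapsible, so the models with and without the term target the same effect. The primary result is not involved.
- *Most of the over-dispersion would be explained by the baseline count.* In the 4-week simulations the variance was never halved. It was halved only at the 0.9 ceiling with a 3-month count.
- *Major and minor events are affected alike.* The sparse major counts rule this out.

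**What to change.** Before unblinding, amend SAP 2.4.2 as follows.

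1. Add log((Visit 1 pre-randomisation count + 0.5)/length of its recall window) as a covariate. Use the minor count in the minor-event model, where the gain lies, and the major count in the major-event model, where little gain is expected. Keep the collection-method term for minor events.
2. Define the baseline window as the time from the recorded date of the last contact at which hypoglycaemia was asked about to Visit 1.
3. Where the Visit 1 count or window is unavailable, use a missing-indicator. The general fallback to R1 data in SAP 1.6.2 should not apply to this covariate, because the R1 count has no defined window.
4. Report the rate ratio without the baseline term as supportive.

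The cost is a short SAP paragraph and the derivation of one date interval per participant. No new data are needed. Specifying it in advance matters because a baseline term added after unblinding would look data-driven.
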